at Columbia University, New York University, and Northwell Health. The Platform is designed for intervention, adaptability, and customization and can be used to manage multiple forms of participant contact, including email, text, and phone/voice chat. The platform also accommodates linkages to online surveys (such as through Qualtrics) to collect more extensive assessment data. The Platform is hosted in HIPAA-compliant Amazon Web Services, with messaging triggered through Twilio, and is managed by Partnership to End Addiction's staff of content and programming experts.

All contacts between study staff and participants will go through the Platform. Partnership to End Addiction's IT department will create a Platform account for the study, with a dedicated phone number, that will be accessible only to the PI and study RAs. Upon enrollment into the study, home visitors and clients will be instructed to send a text message to the study phone number, which will enroll them into the Platform. This will allow study staff to send communications via text message. Upon enrollment into the Platform, participants will receive an automated message asking them to select preferences for language (English or Spanish) and correspondence via text or email (with a prompt to enter their email if selected). Communications with home visitors will include (1) reminders to complete study activities; and (2) brief fidelity questionnaires as described above. Communications with clients will include (1) reminders to complete study activities; and (2) scheduling assessments; and (3) technical support requests and responses. Secure links to e-SBI components and online assessments will also be sent at the time when clients should complete them. Home visitors and clients can also text and/or call the study team to ask questions, reschedule assessments, or request technical support. Some messages will be automated (i.e., the welcome and initial introductory messages) and others will be generated in real-time by study RAs, using pre-written text to ensure consistency in messaging across RAs.

Implementation Data Collection

Qualitative feasibility interviews (approx. 30 minutes) will be conducted via zoom with all home visitors and a random sample of 10 clients (balancing on pregnancy status) in the intervention condition during the second half of the pilot RCT to assess feasibility and acceptability of the SBI-HV. We will randomly select 10 clients to participate in the interview. Selection will be random with one exception: we will ensure that the proportion of pregnant women in the interview sample of 10 is representative of the proportion of pregnant women in the overall sample. Thus, if the overall sample of 20 women in the experimental condition includes 8 pregnant women, we will randomly select 6 non-pregnant women and 4 pregnant women to participate in the interviews. All interviews will be one-on-one. Clients and home visitors will be interviewed separately. All qualitative interviews will be recorded and transcribed, in accordance with gold standard procedures for collection and analysis of qualitative interview data. While we prefer that clients and home visitors have their video cameras on during the interview to allow for a more natural conversation, clients and home visitors will have the option to leave their cameras off and join with audio only if they are more comfortable with that. Recordings of qualitative interviews will include audio only, using the setting on Zoom that allows for recording of audio only without video. Thus, no recordings will include video. If a participant is not comfortable being recorded, they can still participate in the interview; the interviewer will take detailed notes on what is said. Clients will also complete a series of quantitative rating scales at the end of each e-SBI session assessing user satisfaction. Home visitor fidelity will be assessed via brief questions delivered via text message following virtual visits in which facilitation protocols are intended to be implemented. Home visitors will also be asked to complete a brief Qualtrics survey prior to SBI-HV training to assess demographics and readiness to implement evidence-based interventions.

Outcome Data Collection

Client outcome data will be collected at baseline, 3- and 6-month follow-up using validated clinical assessment instruments. Assessments will be conducted either via online survey using Qualtrics, or via phone or video-conference with the study RA, depending on the client's preference. Video-conference data collection will be done over Zoom and these sessions will not be recorded. Assessments will be available in English or Spanish. Each assessment will take approximately 40 minutes and clients will receive \$25 per interview completed. To maximize our follow-up rates, we will obtain multiple forms of contact information and contact the home visitor when unable to reach clients directly. Strategies proven effective for maximizing honest disclosure of substance use in high-risk populations will be applied, including: option for completing the survey online without the RA, a Certificate of Confidentiality, and numeric ID codes to link within-client data across timepoints without attaching client identifiers to responses.

STUDY MEASURES

Feasibility and Acceptability

Feasibility and acceptability of SBI-HV will be assessed via qualitative interviews with home visitors and clients in the intervention condition, designed based on published guidelines for assessing feasibility and acceptability of new interventions in field settings. Home visitor interviews will assess added burden of the SBI-HV, perceived benefits, and implementation barriers. Client interviews will focus on e-SBI satisfaction, barriers to discussing SU with home visitors, and the impact of the e-SBI on their HV experience. Following completion of the e-SBI sessions, clients will complete several quantitative items assessing different dimensions of user satisfaction. Finally, completion rates for each e-SBI session will be used as indicators of feasibility.

Home Visitor Measures

Prior to SBI-HV training, home visitors in both conditions will complete a brief demographic survey. They will also complete the *Evidence-Based Practice Attitude Scale*, a 15-item measure of provider attitudes towards evidence based practices (EPBs), that generates 4 scales: Appeal of EBPs, Required Use by Organization, Openness to Trying EBPs, Unfavorable Attitudes toward EBPs. Consistent factor structure and good internal consistency have been shown in diverse provider samples. Home visitors will complete 1-2 item brief fidelity checklists after each visit in which a facilitation protocol is intended to be implemented. These items will be sent to home visitors via text message and they will respond via text message.

Client Measures

Clients will complete a battery of assessments at baseline, 3-month, and 6-month follow-up using instruments that have demonstrated strong psychometric properties in similar samples. At baseline, we will administer selected sections of the *Addiction Severity Index (ASI)* to assess basic demographics and lifetime and current problems with physical health, employment and finances, illegal activity, family relationships, and psychiatric symptoms. Trauma history will be assessed at baseline via the *Childhood Trauma Questionnaire-Short Form*. Primary study outcomes (to be assessed at baseline, 3-mo, and 6-mo follow-up) include substance use, depression, and parenting stress. Substance use will be assessed via the *Timeline Follow Back Interview*, a calendar-based method for assessing quantity and frequency of SU. Primary SU outcomes will include seven-day point-prevalence abstinence rates and monthly reported days of use. Depression will be assessed via the *Beck Depression Inventory-II*, a 21-item scale measuring depressive symptoms that is widely used in research and practice with perinatal women. Parenting stress will be assessed using the *Parenting Stress Index-Short Form*, a 36-

item measure of stress associated with parenting that is widely used in longitudinal studies of parenting and HV. Secondary study outcomes (assessed at baseline, 3-mo, and 6-mo follow-up) include home visiting retention, home visitor-client relationship, substance use treatment engagement, child protective services reports, and conversations about substance use during home visits. HV retention, CPS reports, and conversations about SU will be mined from the HFA MIS. SU Treatment Engagement will be assessed at 6-month follow-up via the *Treatment Services Review*. Additional variables that are potential moderators of impact include: motivation to change, intimate partner violence, social support, and stress. Motivation to change substance use will be measured with the Maternal Motivation Scale. Intimate partner violence will be measured with the Composite Abuse Scale. Social support will be measured with the Interpersonal Support Evaluation List (ISEL-12), and stress will be measured with the Perceived Stress Scale. All are validated measures that have been widely used in other studies of pregnant and postpartum women. The strength of the relationship between home visitors and clients will be measured via the Working Alliance Inventory-Short Form, Client Version (WAI-SC). The WAI-SC is a 12-item measure of client perceptions of trust in their provider and of agreement on goals and tasks, and has demonstrated good psychometric properties in the HV context.

DATA ANALYSIS

Feasibility, Acceptability, and Fidelity. We will use thematic content analysis to analyze qualitative data, an approach that applies inductive coding to identify themes within the data, and has been used in other evaluation studies in child welfare, including our prior HV study. Audio-recordings of interviews will be transcribed verbatim and transcripts will be coded by two independent raters. Final themes will be determined via an iterative process of individual rater review and discussion to resolve discrepancies, according to the following steps: (1) independent transcript review by each rater to note general themes and highlight key concepts; (2) generation of list of lower-level sub-themes and collated statements by each rater independently; (3) review of sub-themes by both raters and consensus decisions on final list; (4) sorting of sub-themes into higher-level thematic categories by each rater; (5) raters come together to agree on final thematic map. Quantitative items assessing client satisfaction with the e-SBI will be analyzed using descriptive statistics in SPSS. We will examine descriptive statistics for all fidelity checklist items to determine dose of home visitor facilitation received.

SBI-HV Impacts on Client Outcomes. The study will use a randomized intent-to-treat design, with home visitors randomly assigned to condition (routine HV vs. HV+SBI-HV). Data will have a 3-level nested structure: clients (N=40) within home visitors (N=10-20) within sites. Given the small number of home visitors and sites, modeling each as a random effect would not yield stable estimates. Therefore, we will use the sandwich variance estimator to adjust standard errors as appropriate to account for nesting of clients within home visitors. Site will be included as a fixed covariate in all models. We will conduct ANOVA or chi-square tests to assess group equivalence on home visitor characteristics (demographics, EBP readiness), and client characteristics; those that differ between groups will be included as covariates. We will conduct latent growth curve (LGC) modeling in Mplus to examine the impact of study condition on change over time in primary and secondary outcomes. Mplus provides full information maximum likelihood estimation that produces unbiased parameter estimates under the assumption that the data are missing at random (MAR), and outperforms other missing data approaches even when MAR is not met. Analyses will use a 2 (study condition) X 3 (time) repeated measures intent-to-treat design. First, we will use likelihood ratio difference tests of nested models to determine the overall shape of the individual change trajectories: no change or linear change. Next, we will test unconditional models for all outcomes to obtain the average change effect. Third, we will add study condition to test its impact on initial status and change over time. Model

fit will be evaluated via chi-square, RMSEA, CFI, and TLI, and condition effects will be demonstrated by a statistically significant slope parameter, as tested by the pseudo z test, associated with study condition. For normally distributed outcomes, we will use conventional LGC models, with the appropriate estimator selected based on the distributional properties of the DVs. If client outcomes deviate substantially from normality, we will apply a negative binomial estimator, as recommended for count outcomes (i.e., days of SU) with a distribution that is skewed toward zero. Effect size estimates using Cohen's d will be calculated for all condition effects on client outcomes based on published LGC model recommendations.

The LGC modeling described above is our preferred approach for analysis. However, given our small sample, we present an alternative analytic strategy in case the longitudinal models fail to converge. If this occurs, we will conduct a series of ANOVAs to test the difference between study conditions on client outcomes separately at each follow-up time point (3- and 6-month), including the baseline value of the outcome as a covariate. Effect sizes will be calculated using Cohen's d .

Exploratory post-hoc analyses using the methods described above will be conducted to examine: (1) condition differences in home visitor-client alliance; and (2) differences in SBI-HV impact based on pregnancy status.

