Home visitors will be randomly assigned to Intervention or Control conditions, and clients will be assigned to whichever condition their home visitor is in. SBI-HV components that will be added on to routine HFA services include (1) electronic screening and brief intervention (e-SBI); (2) Home Visitor Facilitation; and (3) Technical Support. Table 1 details which study component clients in each condition will receive. The primary difference between conditions will be in the content of the e-SBI and home visitor facilitation components. A detailed description of each SBI-HV component follows the table.

Table 1. SBI-HV Components by Study Condition

Intervention Condition	Control Condition
Routine HFA Services	Routine HFA Services
e-SBI Session 1: Substance Use e-SBI Session 2: Co-occurring Problems	e-SBI Session 1: Nutrition e-SBI Session 2: Exercise
Home Visitor Facilitation: Introduction and de-brief before and after each e-SBI session (content related to substance use and co-occurring problems)	Home Visitor Facilitation: Introduction and de-brief before and after each e-SBI session (content related to nutrition and exercise)
Technical support provided by research staff	Technical support provided by research staff

Routine HFA Services

HFA is an evidence-based, voluntary, HV program designed to promote positive parenting, enhance child health and development, and prevent child maltreatment in at-risk families that serves families prenatally up to age 5 years. Home visits (approximately 1 hour each) occur weekly for the first 6 months, tapering in frequency over time depending on the family's level of functioning, and follow a structured curriculum. Model implementation follows the HFA Best Practice Standards, operationalized through structured program guidelines that are flexibly tailored to families' needs. HFA mandates a quality assurance and accreditation process for program sites, thus an infrastructure for fidelity monitoring and CQI is already in place. Federally-funded HFA sites are also required to track and report progress on federally-specified benchmarks. All of the NJ HFA sites are accredited and federally-funded and have extensive data tracking and CQI procedures in place. Home visitors and supervisors routinely complete logs after each visit and supervision session and data is maintained in an electronic Management Information System (MIS) managed by PCANJ.

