The HFA national model requires a minimum of a high school diploma plus relevant experience for home visitors and a Masters degree or BA with 3 years experience for supervisors. Training is required for home visitors (4 days) and supervisors (2 days) at initial hire with annual refreshers. In NJ, all HFA training is provided by PCANJ. As required by the HFA standards, all full-time home visitors receive 2 hours of individual supervision per week. Per the HFA Standards, each supervision session must include administrative (i.e., oversight of program policies; adherence to standards), clinical (i.e., discussing families' challenges; providing guidance and coaching; evaluating progress), and reflective (i.e., attending to home visitors' emotional reactions) components.

Families are eligible for enrollment in HFA if they are prenatal or within 2 weeks of the baby's birth, and if they have two or more risk factors associated with child maltreatment (e.g., inadequate income, unstable housing, history of substance abuse, no prenatal care, history of depression or psychiatric care). Note that these eligibility criteria pertain to enrollment in the HFA program and are different from eligibility criteria to enroll in the research study described in this protocol (detailed on page 3). Supervisors assign clients to home visitors based on the home visitor's experience and skill, difficulty level of the family, and home visitor's current caseload. Home visitor caseload size is 13-26 families, varying based on the service needs of each family.

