RECRUITMENT, ENROLLMENT AND RANDOMIZATION PROCEDURES

Home Visitors

The PI will schedule a group zoom meeting for all HFA home visitors in New Jersey's HFA network to introduce the study. Following that meeting, home visitors who are interested in possibly participating will be invited to schedule a one-on-one zoom meeting with the PI. During the one-on-one meeting, the PI will explain the study in detail and review the informed consent form. A pdf version of the informed consent form will be sent to the home visitor via email prior to the zoom meeting so that they can follow along as the PI reviews it. Home visitors will be given the opportunity to ask questions about the study and the consent form. Once all questions are answered, the PI will ask the home visitor if they would like to make a decision right then whether to enroll or if they would like to take some time to think about it. If the home visitor would like time to think about it, the PI will call the home visitor back at a later time specified by the home visitor. When a home visitor decides to enroll, he/she will sign the pdf version of the consent form via DocuSign and then email it back to the PI. The PI will sign via DocuSign as well and then email a fully signed copy back to the home visitor for their records. Signing the consent form constitutes enrollment into the study. Following enrollment, the PI will use a computerized randomization program to randomly assign home visitors to study condition (Intervention or Control).

Clients

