Clients will be assigned to home visitors according to usual site procedures. Home visitors will introduce the study to all clients who meet eligibility criteria (English or Spanish speaking; 18 or older; pregnant or within 3 months postpartum; enrolled in HFA within the prior 6 months) at the enrollment visit (for newly enrolling clients) or at the next available visit (for clients already enrolled within the prior six months) using a script provided by study staff. Home visitors will ask clients for their permission to provide their contact information to the study team. If permission is granted, the home visitor will provide the client's contact information to a study RA, who will contact the client by phone and conduct a brief eligibility screen (data will be retained anonymously). Home visitors will also give clients the option to contact the study team themselves, if they prefer, rather than having home visitors provide their contact information to the study team. If the client is eligible, the study RA will explain the study in more detail and ask the client if she is interested in enrolling. If the client says yes, the RA will send the client a link to a pdf copy of the informed consent form via email or text (depending on client preference). After giving the client a few minutes to review the consent form, the RA will review the main points in the consent form and ask the client if she has any questions. After answering all questions, the RA will ask the client if she would like to decide now whether or not to enroll, or would like to take more time and receive a call back later from the RA. If the client would like more time, the RA will call the client back at a time specified by the client. Once the client decides to enroll, the RA will ask her to sign the pdf of the consent form using DocuSign and send it back to the RA. The RA will then sign as a witness, and send the pdf to the PI for her signature, also using DocuSign. After obtaining all signatures, the RA will send a final signed pdf of the consent form back to the client for her records. After the informed consent process is complete, the RA will either send the client a link to complete the baseline assessment online (via a Qualtrics survey), or schedule an appointment to complete the baseline assessment with the client via phone or video-conference, depending on the client's preference. Signing informed consent and completing the baseline assessment constitutes enrollment into the study. Clients are assigned to whichever study condition their home visitor is assigned to.

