Timeframe	Activity	Person Responsible
Home Visitor Recruitment, Enrollment, and Training [October 2020-December 2020]		
At Quarterly Supervisors' Meeting in October	HELP staff introduce study to HFA supervisors at Quarterly Supervisors' Meeting (via Zoom)	PI, RAs
Scheduled for Oct-Nov 2020	HELP staff introduce study to home visitors in NJ HFA network (via Zoom)	PI, RAs
	Home visitors sign informed consent and enroll in study via individual Zoom meetings with PI	PI, RAs
	Home visitors are randomized to condition	PI
After home visitors enroll [Dec 2020]	Home visitor training [pre-recorded videos plus live zoom sessions]-intervention and control groups trained separately	PI, RAs, Home visitors
Client Recruitment and Enrollment [January 2021-October 2021]		
At HFA enrollment visit OR next visit after client is identified as eligible	Home visitors introduce study (using script) to all clients meeting eligibility criteria: newly enrolling or enrolled within the last 6 months; speak English or Spanish; 18 years or older; pregnant or within 3 months postpartum.	Home visitors
Weekly	Home visitors provide client contact information to HELP staff	Home visitors
Ongoing	HELP RAs contact client, conduct eligibility screen, and obtain informed consent from eligible clients who are interested in participating.	RAs
Within 1 week of consent	Client completes baseline assessment [either via Qualtrics link or via phone with RA, depending on client preference]	RAs, Clients
Upon completion of baseline	RA informs home visitor that client has enrolled and completed baseline interview and to do Introduction at next home visit (content differs by condition)	RAs
Implementation of HV-SBI Components [January 2021-December 2021]		
At next home visit	Home visitor completes Introduction: Alcohol & Other Drugs (for intervention group) OR Introduction: Nutrition (for control group)	Home visitor
After home visit	RA sends home visitor text-based fidelity checklist to determine whether Introduction was completed	RAs

	Home visitor completes text-based fidelity checklist	Home visitor
Within 2 weeks of baseline	RA prompts client to complete HELP Session 1 (content differs by condition) within 2 weeks of baseline date and provides technical support by phone or text as needed	RAs
Within 2 weeks of baseline	Client completes HELP Session 1	Clients

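### Families are still matched to home visitors by supervisor judgement after the visitors are randomised and trained by arm, so baseline severity can differ between arms in either direction

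*Combined protocol and SAP*

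**What the plan says.** Under Study Conditions, home visitors are the randomised units and "clients will be assigned to whichever condition their home visitor is in". The recruitment section for clients says "Clients will be assigned to home visitors according to usual site procedures". The usual procedure is described under Routine HFA Services: "Supervisors assign clients to home visitors based on the home visitor's experience and skill, difficulty level of the family", and the sentence goes on to name the visitor's present caseload as the third criterion.

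The recruitment section for home visitors has the PI randomise each visitor after consent. The Timeline places visitor enrolment, randomisation and arm-specific training in October-December 2020. It places client recruitment in January-October 2021 and includes families newly entering HFA as well as those who joined in the previous six months. HFA supervisors hear about the study at their October quarterly meeting. No section describes keeping them unaware of visitors' arms, or limits recruitment to families matched before randomisation.

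The Data Analysis section provides three relevant protections. Site is a fixed covariate in all models. Characteristics that differ between groups on ANOVA or chi-square tests become covariates. If the growth models fail to converge, the fallback ANOVA adjusts for the baseline value of the outcome.

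**The concern.** In a cluster trial, randomising the clusters protects the client comparison only if the way clients reach clusters does not depend on allocation. Here a family matched after December 2020 gets her arm from a supervisor's decision, and two of the three stated criteria (visitor skill and family difficulty) may be related to prognosis. If a supervisor counts study training as part of a visitor's skill, or directs certain families towards or away from study visitors, the arms can differ at baseline for reasons other than chance.

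Supervisors could plausibly learn the arms. They are briefed on the study, and each full-time visitor has two hours of individual supervision a week. A history of substance abuse is one of the example risk factors for HFA entry, so it may be known at matching. The matching comes before the visitor introduces the study, so the scripted introduction does not control it.

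At stake is the preliminary comparison of abstinence, days of use, HV retention and CPS reports between arms.

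**Working it through.** The plan gives no figure to reproduce: it states no power, effect size or intracluster correlation, and 40 clients is not derived. The check is of timing, then of the size of a possible imbalance, then of the planned safeguard.

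**1. Share matched after allocation**

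From the plan: visitors randomised and trained by December 2020; client recruitment over 10 months from January 2021; HFA enrolment within the prior six months. Assumed: match date is close to HFA enrolment date, recruitment is even, and tenure at recruitment is uniform over 0-6 months.

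- Recruited July-October 2021 (4 of 10 months): six months back reaches January 2021 at the earliest, so all are matched after allocation. This step does not need the assumptions of even recruitment or uniform tenure.
- Recruited January-June 2021: at t months into recruitment the share matched after December is t/6. Integrated over 0 to 6, this gives 3 client-months out of 6.
- Overall: (3 + 4)/10 = 70%. The remaining 30% of 40 is 12 clients matched before the end of December 2020.

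**2. Size of a possible imbalance**

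The inputs are illustrative and not in the plan: half of clients carry a risk marker known at matching, and supervisors send 60% of the later-matched ones to one arm. The result depends on what happens to the other half.

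- *Others sent 40:60, which keeps arm sizes equal.* Marker share in the favoured arm: 0.30 × 50% + 0.70 × 60% = 57%. In the other arm: 0.30 × 50% + 0.70 × 40% = 43%. Gap: 14 points.
- *Others sent 50:50.* Favoured arm: (0.30 × 0.25 + 0.70 × 0.30)/(0.30 × 0.50 + 0.70 × 0.55) = 0.285/0.535 = 53.3%. Other arm: (0.30 × 0.25 + 0.70 × 0.20)/(0.30 × 0.50 + 0.70 × 0.45) = 0.215/0.465 = 46.2%. Gap: about 7 points.

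The favoured arm may be either one; the arithmetic is symmetric. If marker-positive and marker-negative clients differed by 0.5-0.8 SD in outcome (also assumed), the unadjusted bias would run from 0.07 × 0.5 = 0.035 SD to 0.14 × 0.8 = 0.11 SD.

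**3. Would the planned equivalence test pick it up?**

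Assumed: 20 clients per arm (the qualitative interview example in the plan uses 20 in the intervention arm), two-sided 5% level, normal approximation, no clustering.

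- Standard error under no difference: √(2 × 0.5 × 0.5/20) = 0.158, so significance needs a gap of 1.96 × 0.158 = 31 points.
- 57% v 43%: standard error under the alternative √(2 × 0.57 × 0.43/20) = 0.157; Φ((0.14 − 0.310)/0.157) = 14%.
- 53.3% v 46.2%: Φ((0.070 − 0.310)/0.158) = 6%, or about 7% counting both tails.

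For a continuous baseline measure, the power at 20 per arm is 16% for a true 0.3 SD difference and 35% for 0.5 SD. With an assumed intracluster correlation of 0.10 and four clients per visitor (design effect 1 + 3 × 0.10 = 1.3), these fall to 13% and 28%.

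**The case against.** The strongest reply is that nothing shows steering would occur, and several features of the plan weaken the motive. The brief intervention is fully automated, facilitation takes five minutes from a script and is not meant as therapy, and substance use training is already required of every HFA visitor. Caseload also drives matching. The protocol's own premise is that women conceal use, so supervisors may not know of it. All of this stands. A reader might infer that the usual rule would send higher-risk families to intervention visitors. The documents do not support that direction: they do not say that supervisors are told each visitor's arm or would treat study training as skill. What survives is that a client receives the substance use e-SBI only through an intervention visitor, and nothing prevents that from influencing a match.

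Eligibility narrows the contrast too. Every client must report binge drinking or illicit drug use before pregnancy and not be attending treatment. Steering could therefore shift severity among users, not the presence of use, and a history known at HFA intake is only an imperfect marker of severity.

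The analysis also separates initial status from slope, so a baseline difference in level is not itself counted as a treatment effect. That is a partial protection. If more severe users change at a different rate, the slope is still affected, and the plan does not specify adjusting the slope for initial status. Site as a covariate does not remove steering between visitors within a site.

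A gap of 7-14 points is below one chance standard error (16 points) at this sample size. That limits how much steering alone could mislead a single pilot. Chance imbalance is reflected in the standard error, however, and a systematic shift is not.

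**Conclusion.** The concern holds as a design vulnerability. For families matched after the visitors are randomised, arm depends on a judgement that uses visitor skill, family difficulty and caseload, made by supervisors who are not kept unaware of arm. That covers everyone recruited from July 2021 and about 70% overall, the latter resting on even recruitment and uniform tenure.

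The imbalance could run either way and could differ between sites. The 7-14 point range is an illustration from an unsourced 50% marker prevalence and 60:40 split, not an estimate. The firmer conclusion is that adjustment triggered by baseline tests would usually miss a gap of that size at about 20 per arm.

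The consequence is limited. This is a pilot whose first aim is feasibility, acceptability and fidelity. The note at the front of the document states that randomisation was eliminated, with 4 control and 10 intervention participants, and that the planned longitudinal analyses were not carried out. The point therefore applies to the planned RCT, to any comparison of those 14 participants, and to any reuse of the design. It should not be read as evidence that the enrolled groups were in fact steered.

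**What to change.** 1. State in the client recruitment section, and tell supervisors at the meeting already planned, that study condition and study training are not to be used in matching families during recruitment. Usual procedures otherwise stay unchanged. Do not circulate visitors' arms to supervisors where this can be avoided.
2. Record the date each client was matched to her home visitor.
3. Report baseline Timeline Follow Back use by arm, separately for clients matched before and after randomisation. Keep this descriptive: the earlier subset is only about 12 clients, roughly 6 per arm, and cannot confirm or exclude bias. The Timeline Follow Back is preferable to pre-pregnancy use, which is not clearly available at baseline in both arms: the modified ASSIST sits in intervention session 1, and eligibility-screen data are kept anonymously.
4. Prespecify adjustment for baseline substance use in all outcome models, whatever the equivalence tests show. In the substance use growth models, do this by regressing the slope on initial status.

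The cost is one instruction, one date per client, one table and one extra model term at N=40. The downsides are a small limit on supervisors' discretion that cannot be fully verified, and some added strain on models the plan already expects may not converge.
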